## **J. Quality Control Method**

Data quality control will be assured through automated and manual methods. The study database enhances data quality through required entry fields for critical data and automatic flags for missing or out-of-range data. Efforts will be made to minimize data entry error by the development of a user-friendly database and all data entry will be double-checked with the source files. Data will be audited for accuracy by investigators after being entered into the database.

## **K. Data Analysis Plan**

At the time of data analysis, de-identified datasets will be downloaded from the secure database and merged into secure statistical analysis tool for purposes of analysis. Missing data will be accounted for when the data is coded into respective variables.

Descriptive statistics will be generated in order to summarize demographic characteristics of patients enrolled. Data will be tested for normality using the Shapiro-Wilk test. Data will be presented as total n (%), means and standard deviations (SD) if the distribution appears normal, or medians and range when not.

Assuming normality, t-tests will be conducted to investigate the differences between the two exposure groups (to compare total opioid equivalents, time required to place the block, time to extubation, and time to discharge, etc.). If data does not appear to be normal, Wilcoxon Rank Sum/Mann-Whitney tests will be used for group comparisons. Repeated measure analysis will be used to compare pain scores over time between groups and when compared to baseline values. Adverse events and complications (if any) associated with the blocks will be recorded and categorized. Fisher's exact test will be used to compare the proportion of patients who reported adverse events between the two groups.  $P<0.05$  will be considered statistically significant.

Should a clinically significant effect be demonstrated, healthcare costs related to the surgical encounter for both groups will be approximated and compared in order to better assess the added value of the intervention in a more global fashion.

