## **L. Sample Size Considerations**

In order to evaluate the efficacy of BESB in this cardiac surgical population compared to those who did not receive blocks, we have defined 'efficacious' as denoting an at least 15% difference in the total opioid consumption at 96hours based on the historical rescue opiate data in the matched cohort. Assuming an alpha of 5%, 80% power, and the mean opiate requirements found in our pilot study, we estimate that a total sample size of 38 patients undergoing sternotomy with BESBs and 76 matched controls are needed to demonstrate efficacy of the new treatment (BESB).

**Table 1** (below) demonstrates that, using a 1:2 ratio of BESB:standard ERAS patients, 38 BESB and 76 standard ERAS patients are required to detect a 0.18 mean difference (15% relative reduction associated with BESB) in square-root Total (96-hr) OME between groups with 80% power using a two-sided 0.05-level test. Because the coefficient of variation for 48-hour OME is somewhat smaller, this sample size will provide 87% power to detect a 15% relative reduction (0.16 mean difference) in square-root 48-hr OME between groups using a two-sided 0.05-level test.

Because the larger SD of the two groups from background data (see **Table 2**) was used in these calculations, and because the groups will be matched on several patient characteristics which will minimize variation, these assumptions are conservative and power to detect the effect sizes shown in Table 1 may be even higher than shown.

**Table 1. Required Sample Size to Detect BESB vs. ERAS Group (1:2 Ratio) Reductions in 48- and 96-hour OME (square-root transformed) assuming two-sided  $\alpha=0.05$ , 80%/85% Power, 48-hour mean sqrt OME 1.05 and 96-hour mean sqrt OME 1.23 in ERAS Group.**

Outcome (sq. root)	SD	%Reduction	Group Difference	Power	BESB N	ERAS N
48 hr OME	0.26	15%	0.16	80%	32	64
48 hr OME	0.26	15%	0.16	85%	36	72
48 hr OME	0.26	20%	0.21	80%	19	38
48 hr OME	0.26	20%	0.21	85%	21	42
96 hr OME	0.32	15%	0.18	80%	38	76
96 hr OME	0.32	15%	0.18	85%	43	86
96 hr OME	0.32	20%	0.25	80%	20	40
96 hr OME	0.32	20%	0.25	85%	23	46

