**Table 2. Background Data**

Group	N	Obs	Variable	N	Mean	Std Dev	Median
ERAS	20	sqD0N0D1N1	20	1.050	0.181	1.049	
		sqtotolome	20	1.231	0.211	1.227	
		D0N0D1N1_OME	20	1.134	0.390	1.100	
		Total_OME	20	1.557	0.540	1.505	
BESB	10	sqD0N0D1N1	10	0.890	0.261	0.898	
		sqtotolome	10	1.120	0.320	1.157	
		D0N0D1N1_OME	10	0.854	0.528	0.810	
		Total_OME	10	1.346	0.724	1.340	

Given the possibility of patient withdrawal due to procedural changes, intraoperative exclusionary events, etc., we plan to enroll 45 patients for the BESB intervention group and 90 matched historical controls from the cardiac ERAS database (IRB P00029161).

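### Section L sizes the study on square-root OME, but Section K names no transform and lets a Shapiro-Wilk pretest choose the test; the 15% is also not tied to one scale

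*Combined protocol and SAP*

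**What the plan says.** Section L (Sample Size Considerations) fixes 38 BESB and 76 ERAS patients to "detect a 0.18 mean difference (15% relative reduction associated with BESB) in square-root Total (96-hr) OME between groups with 80% power". The table title gives the control values as "48-hour mean sqrt OME 1.05 and 96-hour mean sqrt OME 1.23 in ERAS Group", and every row of Table 1 is on the square-root scale. The SD is the "larger SD of the two groups from background data". For 96 hours that is the BESB pilot value of 0.320 in Table 2 ("sqtotolome 10 1.120 0.320 1.157"). Table 2 lists square-root and untransformed OME as separate variables.

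Section K (Data Analysis Plan) compares total opioid equivalents between groups and names no transform. The test depends on the data: "Data will be tested for normality using the Shapiro-Wilk test", t-tests follow if normality is accepted, and otherwise "If data does not appear to be normal, Wilcoxon Rank Sum/Mann-Whitney tests will be used for group comparisons". Section K gives no cut-off for Shapiro-Wilk and does not say whether it is applied by group or to pooled data. It does not say whether the t-test assumes equal variances.

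The hypothesis in Section A and the definition of efficacious that opens Section L both state the 15% in terms of opioid consumption, with no square root. Section E lists the primary endpoint over five time windows, also without a transform.

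**The concern.** The sample size belongs to one analysis and the analysis plan describes another. The team chose the square root when sizing from the pilot data, but the transform does not carry over to the plan for the trial data. The primary test is left to a pretest on the outcome data, and that pretest could select different tests for different time windows.

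Two things are at stake. First, efficacy is defined as a percentage reduction. If the rank test is selected, the plan provides a p-value with medians and ranges, but no estimated difference with an interval to hold against 15%. Second, someone reading the hypothesis would take the 80% power to apply to a 15% cut in opioid consumption. It applies to a 15% cut in its square root, which is a much larger effect on consumption.

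**Working it through.** **1. The plan's own figures.** For a two-sample t-test, d = difference / SD, the noncentrality is d × √(n₁n₀/(n₁+n₀)), and df = n₁+n₀−2. The multiplier is √(38×76/114) = 5.033 at 38/76 and √(45×90/135) = 5.477 at 45/90.

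| Outcome | d | n | Noncentrality | Power |
|---|---|---|---|---|
| sqrt 96 h | 0.18/0.32 = 0.5625 | 38/76 | 2.83 | 80.1% |
| sqrt 96 h | 0.5625 | 45/90 | 3.08 | 86.4% |
| sqrt 48 h | 0.16/0.26 = 0.615 | 38/76 | 3.10 | 86.7% (stated 87%) |

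All eight rows of Table 1 reproduce within 2 patients. Section L says only "with 80% power using a two-sided 0.05-level test"; that this is a t-test is inferred from the match.

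**2. How often the pretest would select Wilcoxon.** Assumptions not in the documents: square-root OME is normal, the Shapiro-Wilk cut-off is 0.05, and OME is analysed untransformed. Simulated at 38/76 with a 15% reduction on the square-root scale:

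- SD 0.32 in both groups (the sizing assumption): both groups pass in about 17% of trials.
- Pilot SDs (BESB 0.32, ERAS 0.211): both groups pass in about 35%.
- Pooling the groups before testing gives about 7% and 69% respectively, so the unstated by-group or pooled choice matters.

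**3. Power of the candidate tests.** At 38/76, with a 15% square-root reduction and SD 0.32 in both groups: square-root t 82%, raw t 80%, Wilcoxon 80%, pretest rule 80-81%.

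**4. Rejection at equal square-root means, pilot SDs, 38/76.** Nominal level 5%:

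| Rule | Rejection |
|---|---|
| Unequal-variance t, sqrt OME | about 5% |
| Pooled-variance t, sqrt OME | about 8% |
| Pooled-variance t, raw OME | about 11% |
| Pretest by group, then pooled t or Wilcoxon | about 8-9% |
| Pretest on pooled data, then pooled t or Wilcoxon | about 6-7% |

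Raw means are not exactly equal here. They are 1.231² + 0.32² = 1.618 and 1.231² + 0.211² = 1.560, a difference of 3.7%. The figures for raw-scale tests are therefore not pure type I errors for raw OME.

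**5. What 15% means on each scale.** If every value scales by one factor, a 15% cut in square-root OME is 1 − 0.85² = 27.75% in OME. With the SD held at 0.32, mean OME goes from 1.23² + 0.32² = 1.615 to (0.85×1.23)² + 0.32² = 1.195, a cut of 26.0%. The 48-hour pilot data in Table 2 show the same pattern without any distributional assumption: 1 − 0.890/1.050 = 15.2% on the square-root scale and 1 − 0.854/1.134 = 24.7% in OME.

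**6. Power for a 15% cut in OME itself.** The difference is 0.15 × 1.557 = 0.234, tested by raw t-test:

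| SD (Table 2) | d | Power 38/76 | Power 45/90 | N for 80% |
|---|---|---|---|---|
| 0.724 (BESB) | 0.323 | 36% | 42% | 114 + 228 |
| 0.540 (ERAS) | 0.432 | 58% | 65% | 64 + 128 |

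The square-root t-test does no better. A 15% cut in OME is only about 8% on that scale (1 − √0.85 = 7.8%), with power of about 32-36% at 38/76.

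**The case against.** **Section K is silent on scale, so it may not mean raw OME.** This is fair. Sections K and L belong to one document, and Table 1 labels its outcome as square-root. If Section K were applied to square-root OME, that variable would usually pass Shapiro-Wilk when it is in fact normal, and the sized t-test would be run. A reader might infer that the sized test will certainly not be run; the text does not establish that. What stands is that the primary analysis is not stated and rests on a data-dependent choice.

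**The stated power survives.** A reader might infer that the missing transform or the pretest invalidates the 80%. It does not. At the design alternative every test that Section K could select has about 80-82% power (step 3). A reader might also set 36% against 80% and blame the pretest. That would be wrong too: the 36-58% comes entirely from moving the 15% from square-root OME to OME, and naming the square-root t-test does not recover it.

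**The excess rejection is not mainly the pretest's doing.** This is largely true. It arises because the smaller group has the larger pilot SD and a pooled variance is used; a pooled t-test on square-root OME shows about 8% as well. It also rests on SDs from 10 and 20 patients. The remedy must therefore name the unequal-variance form, and not merely the transform.

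**A percentage can be had without a t-test.** Section K reports medians when data are non-normal, so a percent difference in medians could be calculated. No interval is planned for it, and none is planned under the t-test either.

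**Conclusion.** The point holds as a mismatch between Sections K and L that should be repaired before analysis. The calculations in Section L are correct for a t-test on square-root OME, but Section K does not commit to that analysis and plans no estimate with an interval for the 15% criterion.

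The power cost of test choice is negligible, 1-2 points under the sizing assumptions. The measurable gain from fixing the test is in error control: about 5% rejection rather than 8-9%, if the SDs differ as in the pilot, the pretest is applied by group, and a pooled t-test is used.

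The larger numerical issue is the separate one of scale. The 80% power is for roughly a 26-28% cut in OME. For a 15% cut in OME, as the hypothesis and the definition of efficacious are worded, raw t-test power is 36-58% at 38/76 and 42-65% at 45/90, depending on which pilot SD applies.

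The simulation results assume normal square-root OME and a 0.05 Shapiro-Wilk cut-off. All of the calculations ignore the 1:2 matching, as Section L's sizing appears to do.

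**What to change.** **Section K.** Name one primary analysis: square-root total 96-hour OME compared by an unequal-variance t-test, or by a model that respects the matched sets. Report the mean difference, the percent reduction and a 95% CI, and say how the percent reduction and its interval are calculated. Remove the Shapiro-Wilk step for opioid outcomes and keep Wilcoxon as a stated sensitivity analysis. Align Section E, whose five windows do not literally include the cumulative 96-hour total.

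**Section L.** State that the 15% and the 80% power refer to the square-root scale, and give the equivalent reduction in OME (about 26-28%). Word the hypothesis and the definition of efficacious to match.

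**Cost.** Wording only; no new data and no change to 45/90. If the team instead wants 80% power for a 15% cut in OME itself, no choice of test among those considered provides it at this size. On the pilot SDs a raw t-test would need about 64 + 128 to 114 + 228 patients.

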## **D. Design and Methods**

### **(1) Study Design**

We propose a single arm, open label, interventional study to compare the opiate requirements of 45 patients who consent to receive BESB catheters following cardiac surgery via sternotomy versus 90 matched historical controls who had similar surgical procedures but without BESBs.

Patients meeting eligibility criteria will be recruited and enrolled to have BESBs placed for postoperative pain control as a part of their perioperative anesthetic

plan. These patients will subsequently have a variety of preoperative demographic and functional data collected as well as data related to their surgeries and postoperative course all collected for later analysis. This enrolled group of patients will subsequently be compared regarding these outcome measures with a 1:2 matched, retrospective analysis of patients in the cardiac surgical ERAS program who did not receive regional blocks as a component of their anesthetic care. (The ERAS Cardiac program is a heart center perioperative evidence-based quality initiative. Retrospective data analysis of outcomes for patients in this program is performed for quality improvement purposes and outcomes research [IRB P00029161 – PI: [name] MD, co-investigators: [name] MD, [name] MD]). Children aged 2 years through 17 years meeting entry criteria will be screened and recruited for participation from the Boston Children's Hospital cardiac surgical program.

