### **(3) Description of Study Treatments or Exposures/Predictors**

Participants will have their medical record reviewed following enrollment for demographic information including: gender, age, weight and height, procedure, surgeon, and current and historical medication use.

Any other routine standard-of-care data will be collected preoperatively as well in addition to research-specific data points.

All enrolled patients will have bilateral erector spinae blocks (with catheters for postoperative local anesthetic infusion) placed by the by a member of the BCH regional anesthesia team (under the supervision of a member of the research team) in a sterile fashion after the cardiac surgical procedure is completed. The placement is as follows:

- The patient is placed in a lateral decubitus position (left or right), with all pressure points padded in routine fashion.
- The area for intervention is prepped with a chlorhexidine solution, and sterile drapes are applied to demarcate the block placement area.
- The T4/5 transverse process on one side is identified with the ultrasound transducer in a parasagittal orientation.
- An 18g Tuohy needle is advanced to the target area under direct ultrasound visualization. The needle tip is advanced until it contacts the transverse process, just below the erector spinae muscle complex.
- Normal saline is injected to confirm appropriate needle tip position. The erector spinae muscle is visualized to be elevated up off of the transverse process with normal saline injection
- With confirmation of appropriate needle tip position, the initial local anesthetic bolus is injected using a standard, weight-based dosing protocol.

- Following the bolus injection, a catheter is threaded into the space occupied by the local anesthetic bolus.
- Catheter tip position is verified by one or more of the following: ultrasound visualization of the catheter tip, ultrasound visualization of instilled normal saline and/or ultrasound visualization of a small hyperechoic (i.e. bright on ultrasound) injection of air.
- With the catheter tip position identified, the catheter is tunneled to a cutaneous exit point approximately 2-3cm from the incision using a Crawford needle.
- The catheter is dressed in standard fashion with an adhesive catheter anchor, Dermabond, Mastisol, Tegaderm and tape.
- This is repeated for the contralateral side. To the extent possible, this will be done without repositioning in a contralateral decubitus position.

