- A label indicating that each catheter is a nerve-block catheter with its laterality and date of placement noted is applied to each catheter.
- Catheter placement is complete.
- Postoperative infusion of local anesthetic (ropivacaine) via the nerve block catheter is initiated and managed by the Acute Pain Service (per standardized, clinical weight-based protocols).
- Procedural notes:
  - Minor deviations from the above procedure (e.g. small changes in sequence, needle entrance locations, amount of catheter deployed, etc.) are possible as the anatomy, positioning, etc. of individual patients varies. This is anticipated and allowable so long as such modifications remain within what is currently considered standard of care for the placement of these blocks and what is done in a given case is considered the appropriate standard of clinical care for that patient by the clinical providers placing the block(s).

All patients will have access to the multimodal pain regimen which is standard of care for all ERAS Cardiac patient and includes acetaminophen and ketorolac, when otherwise not contraindicated, as well as pain-score based opiate rescue medications as needed. All patients have access to postoperative pain management as needed by means of a standard opioid-based PCA/NCA demand protocols utilized at BCH if needed. In addition, all enrolled patients will be followed by the Acute Pain Service at BCH as is the standard of care for all patients receiving nerve blocks, enabling access to additional assessment, catheter and infusion management (where appropriate) and opioid treatment as needed 24 hours a day, 7 days a week. In addition, one of the primary investigators will be available to the

Acute Pain Service staff for consultation 24 hours a day regarding any desired consultation on study patients.

Possible risks related to the block include bleeding, infection, local anesthetic systemic toxicity, local anesthetic insensitivity and incomplete block and/or block failure. These risks occur at no greater (or lesser) frequency than when associated with the use of such blocks in routine clinical situations.

Intraoperative and postoperative anesthetic and surgical data, routinely collected for the Society of Thoracic Surgery (STS), will be collected from the EMR.

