In addition to observational tools and subjective scoring, patient functional status (activity, sleep quality and other measures) will be assessed by actigraphic analysis using the Fitbit™ Charge 3 smartwatch. A Fitbit™ will be placed on the non-dominant arm, if possible, after extubation on the day of surgery. The Fitbit™ will remain on the patient until discharge from the hospital (which on average is about 5 days post-op) and the actigraphic data subsequently will be downloaded to the secure research database and the data wiped from the device. If a study subject had an unforeseeable complication and they no longer progressed along the standard recovery path (e.g. re-intubation, return to ICU), or if the watch was interfering in clinical care in any way, the Fitbit™ would be removed.

Following primary data collection for the enrolled subjects, each subject will be matched by surgical procedure using the STS procedure code, to 2 patients within the cardiac surgery ERAS program QI database (IRB #P00029161 which allows retrospective data analysis of outcomes) by the research team. All patients recruited for this study are themselves already part of the enhanced recovery after cardiac surgery clinical program [QIP]. Matching will be performed 1:2 with respect to surgical procedure and diagnosis using the STS codes, within 30% of the study patient's age and according to gender (if possible) and will be blinded to outcomes. Thus, up to 90 additional patients will be included in this study, retrospectively in addition to the 45 study patients from the single arm interventional cohort study (BESB).

Groups will be compared for demographic data, risk factors (from the STS database), diagnosis, procedure and cardiopulmonary bypass and clamp times to ensure their similarities

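### The non-randomised 1:2 matched comparison is tested without covariates or matched sets, so residual imbalance passes into the effect estimate and the standard error may be miscalibrated

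*Combined protocol and SAP*

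**What the plan says.** Section D(1) describes the comparison as a "1:2 matched, retrospective analysis of patients in the cardiac surgical ERAS program who did not receive regional blocks". The BESB arm is prospective and the controls are historical, so treatment is not randomised.

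Section D(3) sets the matching: "Matching will be performed 1:2 with respect to surgical procedure and diagnosis using the STS codes, within 30% of the study" (the percentage is a tolerance on age, relative to the enrolled child). For the remaining factor it says only "according to gender (if possible) and will be blinded to outcomes". It then says the groups will be compared on demographics, STS risk factors, diagnosis, procedure and "cardiopulmonary bypass and clamp times to ensure their similarities". It states no action if they differ.

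For opioid use, Section K offers two tests. The first is "Assuming normality, t-tests will be conducted to investigate the differences between the two exposure groups". Otherwise, "Wilcoxon Rank Sum/Mann-Whitney tests will be used for group comparisons". It does not say whether the t-test is pooled or Welch. The only model-type analysis is a repeated-measures analysis of pain scores, which does not cover opioid use. No section supplies covariate adjustment, a propensity method, a paired or stratified test, or a matched-set term.

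Section L nevertheless argues that matching will reduce variation, so that true power may exceed the tabulated power.

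**The concern.** Matching controls procedure and diagnosis well, but other measured factors only partly or not at all. Under the 30% rule a 10-year-old may be given controls aged 7 to 13 (10 × 0.7 and 10 × 1.3). Weight, STS risk factors, bypass time and clamp time are left to chance and to selection. The control-selection text in Section D(3) also does not say that the exclusion for intraoperative instability or bleeding is applied to controls, so the groups could differ in intraoperative factors.

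If any such factor predicts opioid use, its imbalance becomes part of the estimated BESB effect. The planned balance check would show the problem without correcting it. Choosing covariates after seeing the results of an open-label study would be a poor substitute for naming them now. Section N says the results may be used to develop a randomised trial, so a biased estimate could carry into that trial's planning.

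The secondary issue is the standard error. A test for independent samples ignores correlation within matched sets, and so forgoes much of the precision that Section L credits to matching.

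**Working it through.** **Inputs from the documents.** Target difference 0.18 on square-root 96-hr OME (15% × 1.23 = 0.1845); SD 0.32; 38 BESB and 76 controls needed, 45 and 90 planned; Table 2 SDs 0.320 (BESB, n = 10) and 0.211 (ERAS, n = 20). **Assumed, because the documents do not give them:** set correlation ρ (0 to 0.5), covariate imbalance, and covariate–outcome correlation.

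**1. The plan's own figure.** A two-sample t calculation with difference 0.18, SD 0.32, two-sided 0.05 and ratio 1:2 gives 38/76 with 80.1% power (86.4% at 45/90). The plan's size is reproduced, and it comes from an unmatched, unadjusted test.

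**2. Bias from residual imbalance.** Bias = imbalance (in SDs) × correlation with outcome × 0.32. The false-positive rates are simulated at 38/76 with ρ = 0.1, no true effect and one confounder (20,000 runs for the planned test).

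| Imbalance, correlation | Bias | Share of 0.18 | Planned test | Model with the factor | Model without it |
|---|---|---|---|---|---|
| 0.3, 0.3 | 0.3 × 0.3 × 0.32 = 0.029 | 16% | 6.3% | about 5% | 7.5% |
| 0.5, 0.5 | 0.5 × 0.5 × 0.32 = 0.080 | 44% | 22% | about 5% | 23.5% |

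The last column shows that a set term alone does not help. The confounder has to be in the model.

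**3. Ignoring the sets, equal SDs.** The unpaired test uses SE = 0.32 × √(1/38 + 1/76) = 0.0636. The true SE is 0.0636 × √(1 − ρ), which is 0.0603, 0.0532 and 0.0450 at ρ = 0.1, 0.3 and 0.5. Type I error is about 2 × [1 − Φ(1.96/√(1 − ρ))] = 3.9%, 1.9% and 0.6%.

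**4. Ignoring the sets, Table 2 SDs.** At ρ = 0 the true SE is √(0.320²/38 + 0.211²/76) = 0.0573. The pooled variance is (37 × 0.320² + 75 × 0.211²)/112 = 0.0636, so the pooled SE is √(0.0636 × (1/38 + 1/76)) = 0.0501. The pooled SE is too small, and the formula gives a type I error of about 8%. Simulated values at 38/76 (20,000 runs):

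| Test | SDs | ρ = 0 | 0.1 | 0.3 | 0.5 |
|---|---|---|---|---|---|
| Pooled t | equal | 5.0% | 3.9% | 1.9% | 0.6% |
| Rank-sum | equal | 5.1% | 3.8% | 2.1% | 0.6% |
| Pooled t | Table 2 | 8.6% | 7.2% | 4.5% | 2.1% |
| Rank-sum | Table 2 | 7.0% | 6.0% | 3.7% | 1.9% |
| Welch | Table 2 | 5.0% | 4.1% | 2.3% | 0.9% |

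The Table 2 variance ratio is (0.320/0.211)² = 2.30, with F(9,19) two-sided p = 0.12 and 95% CI 0.80 to 8.5. Equal SDs are therefore not excluded.

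**5. The proposed model.** Random set intercept, four covariates, set-clustered robust SE, t with sets − 1 df, 10,000 runs. Type I error at 38 sets is 4.6% to 5.3%. Power for 0.18 with equal SDs and covariates that do not predict OME:

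| Analysis | ρ = 0 | 0.1 | 0.3 | 0.5 |
|---|---|---|---|---|
| Planned pooled t, 38/76 | 80% | 81% | 84% | 88% |
| Proposed, 38/76 | 77% | 81% | 90% | 97% |
| Planned pooled t, 45/90 | 86.5% | 87.6% | 90.5% | 94.0% |
| Proposed, 45/90 | 84.0% | 87.6% | 94.1% | 98.6% |

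At ρ = 0 and 38/76, covariates explaining 5% of OME variance give 79.5% against 80.5% for the planned test; covariates explaining 10% give 81.4% against 80.0%.

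**The case against.** The best defence is that the design already does much of the work. Both groups come from one hospital's ERAS programme of elective repairs and are matched on procedure and diagnosis, blinded to outcomes. That plausibly narrows bypass and clamp times, and age matching narrows weight. The larger bias case needs a 0.5 SD imbalance and a 0.5 correlation to survive this, and no section supports that. This stands as a limit on size: the bias cannot be quantified from the documents. It does not supply the missing step for whatever imbalance remains.

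Calibration is also a weaker complaint than bias. Positive set correlation is the usual expectation under matching. The excess error needs low correlation, SDs as unequal as in Table 2, and a pooled t-test or, less so, the rank-sum test. This stands too, and the point is secondary.

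The remedy has details to settle:

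- **Cluster correction.** Without a small-sample correction, the robust SE at 38 sets gives about 6–7% type I error; the usual correction restores about 5%.
- **Number of added covariates.** Ten added covariates (an assumed number) cut power to about 73% at zero set correlation, which is tolerable in a sensitivity model only.
- **Incomplete sets.** Section D(3) allows up to 90 controls, so some sets may be incomplete. The simulations assume complete sets.
- **Weight.** Table 2 gives no OME units. If OME is weight-indexed, the case for weight as a covariate changes.

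**Conclusion.** The concern holds. As written, the plan lets imbalance in measured, unmatched or loosely matched factors into the opioid comparison, with no step to remove it. The size is unknown. The 16% to 44% of target and the 6.3% to 22% false positives rest on assumed confounder strength and ρ = 0.1.

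Ignoring the matched sets mostly costs power rather than creating false positives. The exception is a pooled t-test, or to a lesser degree a rank-sum test, at low set correlation with SDs as unequal as in Table 2; Welch is not affected. Planned power is adequate and the sample size need not change. This should be corrected before analysis, but it does not undermine the design.

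**What to change.** In Section K, pre-specify the following:

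1. **Main model.** For square-root total 96-hr OME, the outcome Section L is sized on, and in the same form for each of the five windows in Section E: a linear regression on treatment with a matched-set effect and set-clustered robust standard errors, with the small-sample correction stated. Choose a random or fixed set effect in advance; the two agreed at set correlations 0 and 0.3. State how incomplete sets are handled.
2. **Covariates.** Age, sex, weight and cardiopulmonary bypass time. All are fixed before the block, which Section D(3) places after surgery. State whether OME is weight-indexed.
3. **Balance and sensitivity.** Report standardised differences for every factor compared in Section D(3). Pre-specify one sensitivity model adding clamp time and any STS risk factor whose absolute standardised difference exceeds a stated threshold, for example 0.1. That threshold is inclusive: a balanced, unmatched factor crosses it by chance about 61% of the time at 38/76 (SE 0.199) and 58% at 45/90 (SE 0.183).
4. **Unadjusted comparison.** Keep it as secondary, using Welch if it is a t-test.
5. **Reporting.** Give the adjusted difference with 95% CI on the square-root scale against 0.18. Compute any OME-scale percentage from model-predicted means including the variance term (mean² + variance; for ERAS in Table 2, 1.231² + 0.211² = 1.56 against the tabulated 1.557).

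Which window is primary is a separate matter that this does not settle.

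**Cost.** SAP wording and a little more analysis. Section D(3) already collects "demographic information including: gender, age, weight and height, procedure, surgeon, and current and historical medication use" for participants, adds that "Intraoperative and postoperative anesthetic and surgical data, routinely collected for the Society of Thoracic Surgery (STS), will be collected from the EMR", and plans to compare both groups on these factors. If sets are uncorrelated and the covariates do not predict OME, power falls from 80% to 77% at 38/76 and from 86% to 84% at 45/90. The sensitivity model with two added covariates gives 76% and 83%. Break-even is a set correlation of about 0.1, or covariates explaining roughly 5–10% of OME variance. Unmeasured and calendar-time confounding from historical controls remains and should be stated as a limitation.
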